## **Statistical Analysis**

### *Sample Size and Power*

Given its fluctuating and recurrent nature, delirium presence will be primarily assessed over time with logistic generalized estimating equation models as we have done previously. In brief, time and group will serve as fixed factors, and a group by time interaction term will be included. Interaction terms will be removed from models if no significant interaction effect is observed. These models allow for longitudinal data analysis in the setting of incomplete and missing data. Group models will be constructed individually with the control group serving as a reference. Power calculations were then conducted with generalized estimating equations for the time-averaged difference between two groups (i.e., control group and intervention group, either HELP- or family-based support) in a repeated-measures design with the binary outcome of delirium. Accounting for six equally spaced measurements (twice daily delirium assessments for

the first three postoperative days), with an autoregressive correlation structure (baseline correlation 0.3) and linear missing data structure, a total sample size of 60 patients (n=30 in each intervention group) will provide >80% power to detect a difference in proportions of 15% (approximate Cohen's effect size difference of 0.9) for experiencing an episode of delirium between groups (assuming a baseline proportion of 20% in the control group) with  $\alpha=0.05$ . Power analysis was conducted using PASS 16 (PASS 2019 Power Analysis and Sample Size Software [2019]. NCSS, LLC. Kaysville, Utah, USA, [ncss.com/software/pass](http://ncss.com/software/pass)). As an exploratory analysis, the interaction between HELP- and family-based support groups will be assessed using a generalized estimating equations model.

Descriptive statistics will be reported for secondary and exploratory outcomes. Inferential statistics will be deferred given the small sample size and pilot nature of the trial. Rigorous statistical analysis will be deferred for planned, follow-up, large-scale investigation. However, inferential statistics will be reported for fidelity measures described previously (Outcomes – Protocol Fidelity Measures). For continuous data, the Shapiro-Wilk test will be used to assess for normal distribution, and either independent t-tests or the Mann-Whitney U-test will be used, as appropriate. For categorical data, chi-squared or Fisher's exact test will be used, as appropriate. Cohen's kappa will be used to assess agreement between research-based CAM delirium assessments and FAM-CAM assessments.

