### **Study Overview and Design**

This is a single-center, randomized, factorial pilot trial at Michigan Medicine (Ann Arbor MI, USA). Approval was obtained from the University of Michigan Medical School Institutional Review Board (HUM00165251), and the trial has been registered at [www.clinicaltrials.gov](http://www.clinicaltrials.gov) (NCT04007523). This protocol is also compliant with the Consolidated Standards of Reporting Trials (CONSORT) extension for pilot and feasibility trials and the Standard Protocol Items: Recommendations for Interventional Trials (SPIRIT) Guidelines. Lastly, all study team members are certified in Good Clinical Practice.

After enrollment, patients (n=60) will be allocated (1:1:1:1), via block-randomization, stratified by gender, to one of four groups: usual care (n=15), HELP-based paging system (n=15), family-based paging system (n=15), or both HELP- and family-based paging system (n=15) (Figure 1). The randomization code will be created by the biostatistician (AT) and concealed from the rest of the research team. On the morning of surgery, allocation assignments will be delivered via sequentially numbered, opaque, sealed envelopes to unblinded research team members who will initiate arm-specific operations. The support systems will consist of automated pager alerts to the HELP program and/or family members and caretakers, depending on group allocation, for providing additional delirium evaluation and therapeutic prevention activities (see Interventions – Clinical Decision Support Paging System). Family members in the intervention group will also be provided with preoperative education on delirium and

training in the Family Confusion Assessment Method (FAM-CAM) instrument.

Although it will not be possible to blind patients and family members to family-based interventions, study team members will remain blinded to group allocation during daily assessments. Study flow is illustrated in Figure 1.

**Figure 1.** CONSORT study flow diagram. HELP = Hospital Elder Life program; CAM = Confusion

Assessment Method, LTAC = Long-Term Acute Care

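### The primary GEE on 30 to 60 patients names no standard-error estimator or small-sample correction; with the usual uncorrected sandwich, the 5% test would run at about 5.5–6% (60 patients) or 6.5–7% (30 patients)

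*Combined protocol and SAP*

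**What the plan says.** Under Statistical Analysis, Sample Size and Power, the combined protocol and SAP states that "delirium presence will be primarily assessed over time with logistic generalized estimating equation models". On the model terms, "time and group will serve as fixed factors, and a group by time interaction term will be included"; the interaction is dropped if it is not significant. On the comparisons, "Group models will be constructed individually with the control group serving as a reference".

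Study Overview and Design gives the numbers: "patients (n=60) will be allocated (1:1:1:1), via block-randomization, stratified by gender, to one of four groups", which is 15 per arm. The power statement pools over the factorial: "a total sample size of 60 patients (n=30 in each intervention group) will provide >80% power". The target difference is 15 percentage points, "assuming a baseline proportion of 20% in the control group".

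The plan does not say whether standard errors are model-based or sandwich, whether a small-sample correction applies, or whether the reference is normal or t. An autoregressive correlation appears only in the power calculation, not as the working correlation of the analysis. The one pointer is to the group's own earlier work, which the plan does not reproduce. The paragraph after the power calculation defers inference on secondary and exploratory outcomes because the sample is small, but the primary GEE gets no matching provision.

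**The concern.** The sandwich variance of a GEE is justified as the number of independent patients grows. With 30 or 60 patients it tends to be too small, because it uses fitted residuals that have been pulled towards zero. A Wald test then rejects too often and the intervals are too narrow.

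Two things are at stake: the error rate and interval of the primary outcome, and the precision attached to the effect size that Strengths and Limitations says will inform future power calculations. An unstated estimator also leaves an analyst's choice open on the primary p-value.

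**Working it through.** **Inputs from the plan.** Six assessments per patient; AR(1) correlation 0.3; control rate 20%; difference 15 points, so 5% under intervention; α = 0.05; 30 v 30 for the powered comparison; 15 per arm.

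**Assumptions.** Two-sided test; the 20% is a per-assessment rate; missingness is monotone and linear, reaching 0–50% by the sixth assessment (the plan gives no rate); model with group and time only.

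**Step 1: the plan's own power.** The design effect for a six-point mean under AR(1) is 1 + (2/6) × Σ(6−k)0.3^k for k = 1 to 5, which is 1 + (2/6) × 1.960 = 1.653. Effective observations per group: 30 × 6 / 1.653 = 108.9.

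- Log odds ratio for 20% v 5% = 1.558.
- Variance = 1/(108.9 × 0.2 × 0.8) + 1/(108.9 × 0.05 × 0.95) = 0.0574 + 0.1933 = 0.2507, so SE = 0.501.
- Power = Φ(1.558/0.501 − 1.96) = Φ(1.15) = 87.5%.

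With 20% and 30% missing by the last assessment it is 84.3% and 82.5%. The stated power above 80% is reproduced; on this formula it falls below 80% (to 78%) only at 50% missing.

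**Step 2: type I error under a true null.** Simulation with 6,000 trials per setting, each fitted with a logistic GEE with AR(1) working correlation. The uncorrected sandwich uses the residuals as fitted. Kauermann-Carroll (KC) multiplies each patient's residual vector by (I − H)^(−1/2) and Mancl-DeRouen (MD) by (I − H)^(−1), where H is that patient's leverage block. The t reference has patients minus parameters as degrees of freedom. Monte Carlo error is about 0.3 points. SE/SD is the mean sandwich SE over the empirical SD of the estimate.

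| Groups | Rate | Correlation | Missing at end | Time | Sandwich, z | KC, t | MD, z | MD, t | SE/SD |
|---|---|---|---|---|---|---|---|---|---|
| 30 v 30 | 20% | 0.3 | 0 | linear | 6.0% | 5.1% | 5.3% | 4.6% | 0.965 |
| 30 v 30 | 20% | 0.3 | 30% | linear | 5.5% | 4.5% | 4.5% | 4.1% | 0.983 |
| 30 v 30 | 20% | 0.3 | 30% | categorical | 6.2% | 5.1% | 5.2% | 4.6% | 0.949 |
| 30 v 30 | 20% | 0.6 | 30% | linear | 6.1% | 5.2% | 5.3% | 4.9% | 0.950 |
| 30 v 30 | 12.5% | 0.3 | 30% | linear | 5.6% | 4.7% | 4.7% | 4.3% | 0.962 |
| 15 v 15 | 20% | 0.3 | 0 | linear | 6.4% | 4.5% | 4.8% | 3.8% | 0.939 |
| 15 v 15 | 20% | 0.3 | 30% | linear | 6.7% | 5.0% | 5.2% | 3.9% | 0.926 |
| 15 v 15 | 20% | 0.3 | 30% | categorical | 6.7% | 4.3% | 4.7% | 3.5% | 0.924 |
| 15 v 15 | 20% | 0.6 | 30% | linear | 6.6% | 4.8% | 4.9% | 4.0% | 0.899 |
| 15 v 15 | 5% | 0.3 | 30% | linear | 2.6% | 1.1% | 1.2% | 0.8% | 1.036 |

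As a rough cross-check, an SE that is too small by a factor r gives a rejection rate of 2 × [1 − Φ(1.96r)]. At r = 0.965 this is 5.9% (simulated 6.0%); at r = 0.926 it is 6.9% (simulated 6.7%).

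A separate simulation (4,000 null trials per setting, rates 10–20%, correlation 0.3–0.6) gave 5.4–6.2% at 30 v 30, with SEs 3–4% too small, and 6.4–7.3% at 15 v 15, with SEs 6–11% too small. KC with t gave about 4.6–5.1%.

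**Step 3: rare events at 15 v 15.** In the last row about 11% of trials had no event in at least one group. With complete data, a patient at a 5% rate has no positive assessment with probability 0.95 × 0.965^5 = 0.795, and a 15-patient arm has none with probability 0.795^15 = 3.2%. Missing assessments raise that. The group log odds ratio then has no finite estimate, and no covariance correction repairs it.

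**Step 4: power after correction (20% v 5%).**

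| Groups | Missing at end | Sandwich, z | KC, t | MD, z | MD, t |
|---|---|---|---|---|---|
| 30 v 30 | 0 | 93.4% | 92.2% | 92.4% | 91.6% |
| 30 v 30 | 30% | 89.8% | 87.8% | 87.9% | 86.8% |
| 15 v 15 | 30% | 61.9% | 53.9% | 54.5% | 50.4% |

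The 15 v 15 row excludes the 5.7% of trials with no event in one group.

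**Step 5: the interaction pre-test.** The same unstated estimator decides whether the interaction stays in the model. In a smaller run (1,500 trials) the uncorrected interaction test rejected a true null 5.1–8.5% of the time, depending on time coding and rate, and 3.6–6.8% with correction. At 15 v 15 and a 20% rate about a third of datasets could not support the interaction with categorical time, so that part is conditional.

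**The case against.** The strongest answer is that the plan has not chosen a wrong method. A reader might infer that it uses large-sample sandwich errors because that is a common default, but no sentence says so, and the earlier work it points to is not available here. This stands: the gap is an omission, and every error rate above is conditional on the uncorrected sandwich with a normal reference.

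A reader might also infer that the powered comparison runs at 6–7%, or that the test is always anti-conservative. Neither holds. At 30 v 30 the figure is about 5.5–6%, and at 15 v 15 with a 5% rate, which is the plan's own target for an intervention group, the uncorrected test is conservative at 2.6%.

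Little in the plan turns on a point or so of type I error. Dissemination ties progression to improved HELP practice and family feasibility, not to the delirium p-value. The correction leaves the point estimate unchanged, and MD standard errors are only 3–4% larger than the plain sandwich at 30 v 30 and 7–8% larger at 15 v 15. This stands as a reason to rank the point low.

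Finally, corrections can overshoot: MD with t gives 3.5–4.0% at 15 v 15 and a 20% rate. That argues for a different pairing, not for none, since KC with t and MD with z both stay near 5% at that rate.

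**Conclusion.** The point holds as a minor one. The primary analysis rests on 30 to 60 patients without a stated standard-error estimator or small-sample correction. If the uncorrected sandwich with a normal reference is used, at per-assessment rates of about 10–20% the 5% test runs at about 5.5–6% with 60 patients and about 6.5–7% with 30; standard errors are about 2–5% and 6–11% too small respectively. With rarer events at 15 v 15 the direction can reverse, and groups with no events are the larger difficulty.

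This rests on a two-sided test, the 20% read as a per-assessment rate, up to 30% missing by the sixth assessment and, for the main figures, a model without the interaction. It is more than a missing detail, because a better-calibrated method is readily available.

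**What to change.** State in Sample Size and Power that all GEE tests and intervals, including the interaction test, use a bias-corrected sandwich covariance: Kauermann-Carroll with a t reference on patients minus parameters, or Mancl-DeRouen with a normal reference. Mancl-DeRouen with t should not be the stated choice because it over-corrects at 15 v 15. In the same place, name the working correlation and say what will be reported when a group has no events, for example an exact comparison of the proportion of patients ever CAM-positive.

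The cost is a sentence or two and a software option, with no change to patients or visits. Power falls by about 1–3 points at 30 v 30 and stays above 80% in the simulated settings (up to 30% missing). At 15 v 15 it falls by roughly 5–10 points. Part of that loss is not real, since the uncorrected 61.9% is bought with a test that runs at about 6.7% instead of 5%.

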needed to deliver the interventions, the HELP-based interventions are closely related to usual care, though they may occur sooner and more thoroughly with the pager alerting system. However, there will be some additional resources and training required, particularly for family-based interventions. For (5) flexibility of intervention delivery, pager alerts can be reliably delivered and modified as needed. There are also many opportunities throughout the day to implement clinical protocols as outlined. However, to demonstrate effectiveness, the proposed interventions likely need to occur consistently and with adherence to the protocol. In terms of flexibility adherence (6), daily pager alerts will be reliably and automatically sent to HELP and family members to enhance protocol fidelity. Checklists will also be made available to family members. Follow-up (7) for most outcomes and operations will occur in the immediate postoperative period, and many outcomes described are obtainable via chart review. However, certain follow-up measures (e.g., CAM, 30-day surveys) require prospective collection from research team members, though raters did not raters generally did not anticipate this to be particularly burdensome or prohibitive. Delirium is the primary outcome (8), which is a common and serious postoperative outcome that is relevant to surgical patients. Lastly, the primary analysis plan (9) follows an intention-to-treat approach with longitudinal modeling that accounts for missing data. Although raters generally scored the trial design as pragmatic, raters were part of the trial team, and thus not independent assessors. This may introduce bias with regards to objectively rating explanatory and pragmatic elements of a trial.

**Figure 2. Pragmatic Explanatory Continuum Indicator Summary (PRECIS)-2 tool depicting where RADAR resides on the pragmatic-explanatory trial continuum.** After reviewing training materials, members of the RADAR team independently scored each of the 9 domains included in the PRECIS-2 Toolkit. For each domain, scores range from 1 to 5, with lower scores reflecting an explanatory nature, and higher scores reflecting pragmatic characteristics. Median scores are presented from all team members (n=10) that completed the PRECIS-2 toolkit scoring. The median score for each domain was either a 4 or 5, reflecting a fairly pragmatic study design overall.

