Considerable limitations are also worth discussion. The statistical powering strategy crucially assumes there is no interaction between the interventions (e.g., HELP- and family-based support), which may not be the case. However, this pilot phase will help generate effect size and feasibility data for refining future protocols and power calculations. Next, both HELP officials and family members may be subject to the Hawthorne effect. That is, individuals may modify their behavior under study conditions. Both HELP officials and family members may rigorously perform study protocols knowing that performance is being monitored. As such, protocol effectiveness will likely decrease in non-research settings. For the HELP program, performance measures will be compared to historical controls (2018 HELP records) to mitigate this effect. Family members of patients not randomized to family-based support interventions may still elect to spend more time with patients after learning about the trial and proceeding with enrollment. To assess for latent family support in the control groups, the research team will ask family members about time and activities with patients for comparisons to structured family-based support allocation groups. This will be assessed on the afternoon of postoperative day three, at the end of the inpatient study window, to avoid inadvertent introduction of study-related family support interventions. Additionally, while family members will receive basic training and education on FAM-CAM administration, they will not receive rigorous training for assessing reliability or accuracy. Such training could be pursued in a follow-up trial. Lastly, only patients with family members and/or caretakers – who will be available for the first three days of hospitalization – will be eligible for the trial. Thus, patients without such social support will be ineligible. These eligibility criteria thus exclude a group of

patients who may be particularly vulnerable to delirium (i.e., less social support) and reduce trial pragmatism.

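### The primary delirium model is chosen by an interaction pretest, and no primary group contrast is named if the group-by-time term stays

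*Combined protocol and SAP*

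**What the plan says.** Under Statistical Analysis, Sample Size and Power, the primary model for delirium is a logistic GEE in which "time and group will serve as fixed factors, and a group by time interaction term will be included". The next sentence gives the rule: "Interaction terms will be removed from models if no significant interaction effect is observed". On the comparison between groups it says only "Group models will be constructed individually with the control group serving as a reference".

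The same section sizes the trial on a different footing: "Power calculations were then conducted with generalized estimating equations for the time-averaged difference between two groups". The inputs are six assessments, 30 per compared group, a control proportion of 20%, "power to detect a difference in proportions of 15" percentage points, alpha 0.05, and a working set-up "with an autoregressive correlation structure (baseline correlation 0.3) and linear missing data structure".

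No other section fills the gap. Outcomes defines the primary outcome without a time point or summary measure. The PRECIS-2 discussion adds only that "the primary analysis plan (9) follows an intention-to-treat approach with longitudinal modeling that accounts for missing data". The deferral of inferential statistics covers secondary and exploratory outcomes, not this model. The HELP-by-family interaction is a different term and is labelled exploratory.

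**The concern.** Without group-by-time, the group coefficient is a time-averaged contrast and matches the power calculation. With it, there is no single group effect until one is defined, and at least three readings are open:

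- (i) the average of the six fitted risk differences;
- (ii) the average of the six log odds ratios, which is infinite when any group-by-assessment cell has no positive CAM;
- (iii) the group coefficient at the reference visit, which is a single-visit contrast.

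The choice would be made after the data are seen, and whether it arises at all depends on a pretest whose form is not stated. This matters because Strengths and Limitations says "this pilot phase will help generate effect size and feasibility data for refining future protocols and power calculations". A later trial cannot be sized on an effect that may be a six-visit average, a one-visit contrast, or an odds ratio of 0 or infinity.

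**Working it through.** **Inputs from the plan.** 20% vs 5% (a reduction is assumed), six assessments, AR(1) with correlation 0.3, alpha 0.05 (two-sided assumed), 30 vs 30. Results at 15 vs 15 are also shown, because 30 vs 30 requires pooling factorial arms and the sentence on individually built group models can be read as single-arm comparisons. **Assumed, not in the plan:** interaction level 0.05, and complete data unless stated.

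**Step 1: the plan's own figure.** Information per patient under AR(1) is (6 − 4 × 0.3)/(1 + 0.3) = 3.69 independent observations, so 30 patients give 110.8.

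- Logit scale: log odds ratio = ln(0.20/0.80) − ln(0.05/0.95) = 1.558 in size. SE = √[1/(110.8 × 0.16) + 1/(110.8 × 0.0475)] = 0.496. Power = Φ(1.558/0.496 − 1.96) = 0.88.
- Risk-difference scale: SE = √[(0.16 + 0.0475)/110.8] = 0.0433. Power = Φ(0.15/0.0433 − 1.96) = 0.93.
- With 30% missing at the last assessment: 0.83 and 0.90.
- The stated effect size of about 0.9 is close to 1.558 × √3/π = 0.86.

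The claim of more than 80% stands for the time-averaged contrast.

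**Step 2: how often the term is kept when there is no interaction.** Simulated at 20% vs 5%.

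| Interaction test | 30 vs 30 | 15 vs 15 |
|---|---|---|
| Six-level time, model-based Wald | 0.1% | 0.0% |
| Six-level time, score | 0.6% | 0.0% |
| Linear time, score | 4% | 2% |
| Linear time, robust Wald | about 10% | about 15-24% |
| Six-level time, robust Wald | 58-72% | 65-93% |

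Ranges reflect different working correlations, iteration limits, small-sample scaling and handling of unstable fits.

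The last row is driven by empty cells. At 5%, one cell is empty with probability 0.95^30 = 0.21 or 0.95^15 = 0.46. Some cell is empty in 70% / 95% of simulated trials. When none is, the six-level robust Wald rate is only about 3-6%. It also falls with the group difference: 26% / 75% at 20% vs 10%, and 6% / 35% at 20% vs 20%.

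**Step 3: effect on the group result.**

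- *Reading (iii), linear time, robust Wald, 30 vs 30.* The group effect is taken from the reference visit if the term is kept and from the main-effect model otherwise. Two sets of 20% vs 20% simulations gave null rejection of 0.074 against 0.054 for the fixed main effect, and 0.088 against 0.062. At 20% vs 5%, power was 0.877 against 0.915, and 0.88 against 0.93. The 95% Monte Carlo half-width on a null rate is 1.96 × √(0.054 × 0.946/4000) = 0.007.
- *Reading (i), six-level time, robust Wald.* Detection is 94% / 71% under the rule against 93% / 66% without the interaction, so nothing is lost.
- *Reading (ii), same set-up.* The averaged log odds ratio is infinite in 98% / 99.8% of the trials that keep the term.

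**The case against.** The strongest reply is that the plan powers the time-averaged difference, so that is the natural default. The model is described in brief with reference to earlier work, and this is a pilot. Part of this stands. Dissemination ties progression to HELP practice and family feasibility, not to this estimate. But the default is an inference: the plan states a rule for choosing the model and is silent on one of its two branches.

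Four stronger readings are tempting, and the documents do not support them.

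- *The trial will usually keep a false interaction.* That needs six-level time, a robust Wald test and acceptance of a diverging fit, and the plan specifies none of these. In a rerun with convergence checked, the term was kept in a converged fit in only 0.4-1.4% of trials at 30 vs 30 and 0-0.6% at 15 vs 15. An analyst would usually see the problem.
- *Power collapses to that of a single visit.* The one-visit two-proportion figures (42% at 30 vs 30, 23% at 15 vs 15) apply only to trials that keep the term, and only under reading (iii). They also do not describe the six-level robust Wald analysis. There the reference-visit test is significant in about 39% at 30 vs 30 and 47-50% at 15 vs 15, because an empty cell is itself declared significant.
- *The sample-size claim is wrong.* It reproduces.
- *The risk difference is the one powered scale.* More than 80% is reached on both scales, so either can be defended.

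**Conclusion.** The point holds as a gap in the definition of the primary estimate and should be fixed. The rule lets a pretest decide the primary model and leaves the group contrast unnamed when the term is kept.

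Its size is conditional. With no true interaction, retention ranges from about 0% to about 93% according to choices the plan does not make. The most useful single illustration is linear time with the reference-visit coefficient at 30 vs 30: null rejection of 0.07-0.09 instead of about 0.05-0.06, and power of 0.88 instead of about 0.92-0.93. Averaging the fitted risk differences costs no power.

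These figures rest on the plan's rates and correlation, an assumed 0.05 interaction level, complete data and, for the illustration, an assumed reading of the retained model. The missing contrast does not depend on any of them.

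**What to change.** Delete the test-then-remove sentence and write:

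> The primary estimate is the time-averaged group effect over all six assessments from the logistic GEE with group and time and no group-by-time term, reported with 95% CI whatever the interaction shows. The average risk difference is reported beside it. Group-by-time is exploratory, with delirium counts tabulated by group and assessment.

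This needs no extra patients or visits, and the stated power then applies to the analysis actually done.

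The cost is that a formal interaction test no longer shapes the primary model. Little is given up. In three scenarios with a real interaction, six-level score and model-based Wald tests had 4-31% power at 30 vs 30 and 0-11% at 15 vs 15. A linear-time score test had 28-59% and 16-35% and could be kept as exploratory, with its level stated.

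One weakness remains. At 15 vs 15 the 5% group has no positive CAM at all with probability 0.95^15 × 0.965^75 = 0.03 (0.965 = 1 − 0.05 × (1 − 0.3), the chance of staying negative). The odds ratio is then 0, and the risk difference covers that case.

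A small-sample variance correction is optional and not part of the error.

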Depression and anxiety measures will take place both at preoperative baseline and during postoperative day three (or day of discharge, whichever is sooner). For assessment of falls, study team members will ask about fall occurrences during each study visit, and the medical record will also be reviewed for any falls during the study period. Additional clinical secondary outcomes described will be collected from the electronic medical record. On postoperative day three, for patients not randomized to

the family-support groups, the research team will ask family members about cumulative time spent with patients, and any interactive activities performed, during the first three postoperative days for comparison to family-based intervention groups.

Finally, research data recorded on paper will be stored in participant research records that will be located in locked cabinets in the Department of Anesthesiology at Michigan Medicine. Electronic data will be de-identified and stored online using the REDCap electronic research database, which resides on a secured, password-protected network managed by the Michigan Institute of Clinical and Health Research.

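### The stated power belongs to a 30 vs 30 factorial comparison, but the sentence that specifies the primary delirium models does not define that comparison

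*Combined protocol and SAP*

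**What the plan says.** Study Overview and Design allocates 60 patients 1:1:1:1 to "usual care (n=15), HELP-based paging system (n=15), family-based paging system (n=15), or both HELP- and family-based paging system (n=15"), "via block-randomization, stratified by gender".

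Under Sample Size and Power, delirium over six assessments is modelled by logistic GEE with group, time and their interaction. The rule for the interaction is: "Interaction terms will be removed from models if no significant interaction effect is observed". The comparison is then set by one sentence: "Group models will be constructed individually with the control group serving as a reference".

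The power statement follows in the same paragraph. It concerns the time-averaged difference between "two groups (i.e., control group and intervention group, either HELP- or family-based support"), with "a total sample size of 60 patients (n=30 in each intervention group"), a 15-point difference and more than 80% power, "assuming a baseline proportion of 20% in the control group". It specifies an autoregressive correlation of 0.3 and a linear missing-data structure. It does not state the amount of missing data or whether the test is one- or two-sided. The HELP-by-family interaction is exploratory.

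Two other sections bear on who the controls are. Strengths and Limitations says the powering assumes no interaction between the interventions, and uses the plural, control groups, for patients without family support. Ethical Considerations (Table 4, item 4) says that patients randomised to the control group receive standard care, which describes the usual-care arm.

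**The concern.** The number of patients in the power statement and the models in the analysis sentence do not visibly belong together. A group of 30 arises only by pooling two arms. The analysis sentence mentions no pooling: it builds models one at a time against a single undefined control group. An analyst could fit any of three comparisons and claim to have followed the plan:

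- each intervention arm against usual care, 15 vs 15;
- usual care against everyone who received a given factor, 15 vs 30;
- factor present against factor absent, 30 vs 30.

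Only the last has the sample size on which the power claim rests. Delirium is the primary outcome and the only one with a power claim. If the reference group is left open, it can be chosen after the data are seen, and the precision of the primary estimate depends on that choice.

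**Working it through.** **Inputs from Sample Size and Power:** control proportion 0.20; difference 0.15; alpha 0.05; six assessments; AR(1) correlation ρ = 0.3.

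**Assumptions:**
- The test is two-sided.
- The effect is a fall from 20% to 5%. The plan's own effect size supports this: ln(4.75) × √3/π = 1.558 × 0.551 = 0.86, close to the stated 0.9. A rise to 35% would give 0.42.
- Missingness is monotone and rises linearly from zero at the first assessment. The rate is not stated, so I show none, 20% and 50% missing at the last assessment.

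**Information per patient.** With k assessments under AR(1), I = [k − (k − 2)ρ]/(1 + ρ).
- Complete data: (6 − 1.2)/1.3 = 3.692.
- Each assessment lost from the end removes 0.7/1.3 = 0.538.
- 20% missing at the last assessment: expected loss 0.04 + 0.08 + 0.12 + 0.16 + 0.20 = 0.60 assessments, so I = 3.692 − 0.60 × 0.538 = 3.369.
- 50% missing: expected loss 1.5 assessments, so I = 2.885.

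**Formulas.** Power = Φ(z − 1.96), on two scales:
- log-odds: z = 1.558 / √{[1/(n₁ × 0.16) + 1/(n₂ × 0.0475)]/I}
- risk difference, unpooled variance: z = 0.15 / √{[0.16/n₁ + 0.0475/n₂]/I}

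Here 0.16 = 0.20 × 0.80, 0.0475 = 0.05 × 0.95, n₁ is the control group and n₂ the intervention group.

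**The plan's figure, 30 vs 30, complete data.** z = 3.138 (log-odds) and 3.466 (risk difference), giving 88.1% and 93.4%. The claim of more than 80% reproduces.

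**15 vs 15, complete data.** z = 2.219 and 2.451, giving 60.2% and 68.8%.

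**15 usual care vs 30 exposed, complete data.** z = 2.831 and 2.604, giving 80.8% and 74.0%. A pooled-variance risk-difference test would give about 82%.

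| Comparison | None missing | 20% missing at last | 50% missing at last |
|---|---|---|---|
| 30 vs 30 | 88-93% | 85-91% | 79-87% |
| 15 vs 15 | 60-69% | 56-65% | 50-58% |

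For 15 vs 30 with 20% missing, z = 2.704 and 2.488, giving 77% and 70%.

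**Size needed.** With complete data, 80% power needs (1.96 + 0.842)² = 7.85 times the per-patient variance over the squared effect:
- log-odds: 7.85 × 27.30/(3.692 × 2.428) = 23.9, so 24 per group;
- risk difference: 7.85 × 0.2075/(3.692 × 0.0225) = 19.6, so 20 per group.

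**Robustness.** A one-sided test does not rescue 15 vs 15: 2.219 − 1.645 = 0.574 gives 72%, and 2.451 − 1.645 = 0.806 gives 79%. Simulated AR(1) binary data (20,000 runs, complete data) gave the following:
- 15 vs 15: 65% with a robust Wald test, 59% with a t-correction.
- 30 vs 30: 93% and 92%.

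**The case against.** The strongest reply is that the margins are plainly meant. The power sentence comes straight after the model sentence and in the same paragraph. It describes two groups totalling 60, so its control group must have 30. The no-interaction assumption in Strengths and Limitations makes sense only for a marginal analysis. Data Collection gathers family time from everyone outside the family-support groups "during the first three postoperative days for comparison to family-based intervention groups", which is again a 30 vs 30 comparison. The Ethical Considerations table compresses four arms into two and was not written to define a contrast. All of this stands, and it makes 30 vs 30 the likely intent. It does not amount to a specification, because the sentence that governs the primary models still permits the other comparisons.

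Three stronger readings are tempting, and the documents do not support them.

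- **That the trial is underpowered or the calculation wrong.** The stated figure reproduces. The 60-69% belongs to the least favourable reading, not the most likely one.
- **That the choice of contrast would feed materially different odds ratios into the next trial.** Under the no-interaction assumption the plan already makes, the single-arm and marginal odds ratios nearly coincide. The difference is mainly in precision. Nor is this a go/no-go matter: Dissemination ties the follow-up trial to HELP practice and family feasibility.
- **That margin power falls because half of each control margin receives the other intervention.** This depends on whether 20% is the usual-care rate and on joint effects that the documents do not give. It cannot be sized from the plan.

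**Conclusion.** The point holds as a mismatch between the analysis rule and the power statement, and it should be fixed before data are seen. The claim of more than 80% is right for 30 vs 30 (88-93% with complete data). Separate 15 vs 15 models, which the model sentence literally allows, have about 60-69% with complete data, and no variant of that comparison examined here reaches 80%. The 15 vs 30 reading is borderline at about 74-81% with complete data. These figures rest on a two-sided 0.05 test, a fall from 20% to 5% at each assessment and AR(1) correlation 0.3. The missing-data rows use assumed rates. The consequence is limited to how the primary outcome is estimated and how precisely.

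**What to change.** Replace the model sentence with wording such as: *The primary analysis is one logistic GEE on all 60 patients with HELP (0/1), family (0/1), time and gender (the randomisation stratum). HELP-by-time and family-by-time terms follow the removal rule already stated. The time-averaged HELP and family main effects, each comparing 30 assigned with 30 not assigned, are the primary contrasts. Comparisons of single arms with usual care are descriptive. The HELP-by-family interaction is exploratory.*

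The minimum change, if two separate models are kept, is one sentence defining the control group in each as all patients not assigned that factor (n=30). If 15 vs 15 models are really intended, replace the claim of more than 80% with the 15 vs 15 figure at the planned missingness. In every case, state the sidedness and the missing-data rate beside the power figure.

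The cost is wording only; no extra patients or data are needed. The joint model relies on the no-interaction assumption already acknowledged in Strengths and Limitations, and gender adds one parameter. If time is categorical, by-time terms may be inestimable at assessments with no events. At 5% in 30 patients, the chance of no events at a given assessment is 0.95³⁰ = 21%, and in simulation with correlation 0.3 about 70% of trials had at least one such assessment among six. The current plan shares this weakness, so a fallback, such as time as a linear term, should be named in advance.
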